#### **2.2.3. Summary**

Approximately 125-140 patients are expected to be enrolled in this study (approximately 30-50 patients in Part 1 (actual number of patients enrolled for Part 1 will depend upon tolerability of PF-06747143 and the number of dose levels required to identify the MTD) and approximately 87-102 patients in Part 2). The study will be conducted in approximately 4 sites for Part 1 and approximately 12-15 sites for Part 2.

Patients who complete the maximum number of cycles/months on study treatment (Section 3.1.2.2.1 and Section 3.1.2.2.2), demonstrate clinical benefit with manageable safety profile and are willing to continue receiving the assigned treatment may be given the opportunity to do so upon agreement between Investigator and sponsor and pending investigational product availability.

All patients who completed treatment will have a 60-day post dose follow-up period.

#### 2.3. Study Objectives and Endpoints

#### 2.3.1. Part 1 Study Objectives

#### Primary Objective

• To assess safety and tolerability at increasing dose levels of PF-06747143 in patients with refractory and/or relapsed AML for which no standard therapy is available in order to estimate the Maximum Tolerated Dose (MTD) and select the Recommended Phase 2 Dose (RP2D).

#### Secondary Objectives

- To evaluate the overall safety profile;
- To characterize the single-dose and multiple-dose pharmacokinetics (PK) of PF-06747143 following IV administration;
- To evaluate the immunogenicity of PF-06747143 following repeated administration;
- To document any anti-leukemia activity based on . Diagnosis and management of acute myeloid leukemia in adults: recommendations from an international expert panel, on behalf of the European LeukemiaNet (Ref 2)

[figure not shown]
#### 2.3.2. Endpoints – Part 1

#### **Primary Endpoint**

• Dose Limiting Toxicities (DLTs).

#### Secondary Endpoints

- Adverse Events as characterized by type, frequency, severity (as graded by National Cancer Institute Common Terminology Criteria for Adverse Events (NCI CTCAE) v4.03), timing, seriousness, and relationship to study therapy;
- Laboratory abnormalities as characterized by type, frequency, severity (as graded by NCI CTCAE v.4.03) and timing;
- PK parameters of PF-06747143: Single Dose (SD) Cmax, AUClast, and if data permit, AUCinf, Vd, CL, and  $t_{1/2}$ . Multiple Dose (MD) (assuming steady state is achieved) Cmax, ss, Cmin, ss, AUC $\tau$ , ss, Rac (AUC $\tau$ , ss/AUC $\tau$ , and if data permit, CL, Vss, and  $t_{1/2}$ ;
- Incidence of anti-drug antibodies (ADA) and neutralizing antibodies (Nab) against PF-06747143;
- Preliminary evidence of anti-leukemia activity including objective disease response; as assessed using the standardized response criteria including objective response rate (ORR), duration of ORR, and relapse free survival (RFS).(Ref 2)

## 2.3.3. Objectives – Part 2

#### Primary Objective

• To evaluate safety and tolerability and preliminary anti-leukemia activity (Dohner, et. al 2010)22 of PF-06747143 in combination with standard intensive chemotherapy (ie,

cytarabine and daunorubicin; D/C 7+3) in patients with newly diagnosed fit treatment naïve AML patients (Cohort 1) or with standard dose of decitabine or azecitidine in newly diagnosed unfit treatment naïve AML patients (Cohort 2) or PF-06747143 as a single agent ((Cohort 3) if data warrants).

#### **Secondary Objectives**

- To characterize the single and multiple dose PK of PF-06747143 in combination with standard intensive cytarabine and daunorubicin 7+3 therapy in newly diagnosed fit treatment naïve AML patients or with standard dose of decitabine or azacitidine in newly diagnosed unfit treatment naïve AML patients;
- To collect PF-06747143 drug concentration data in patients from the dose expansion cohorts for evaluation of population PK;
- To evaluate the immunogenicity of PF-06747143 following repeated administration.

#### 2.4. Endpoints – Part 2

#### **Primary Endpoints**

 Adverse Events as characterized by type, frequency, severity (as graded by National Cancer Institute Common Terminology Criteria for Adverse Events (NCI CTCAE) v. 4.03), timing, seriousness, and relationship to study therapy;

- Laboratory abnormalities as characterized by type, frequency, severity (as graded by NCI CTCAE v.4.03) and timing;
- Preliminary evidence of anti-leukemia activity including objective disease response; as assessed using the standardized response criteria including objective response rate (ORR), duration of ORR, and relapse free survival (RFS).(Ref 2)

#### Secondary Endpoints

- PK parameters of PF-06747143: Single Dose (SD)  $C_{max}$ ,  $T_{max}$ ,  $AUC_{last}$ , and if data permit,  $AUC_{inf}$ ,  $V_d$ , CL, and  $t_{1/2}$ . Multiple Dose (MD) (assuming steady state is achieved)  $C_{max, ss}$ ,  $C_{min, ss}$ ,  $AUC_{\tau, ss}$ ,  $R_{ac}$  ( $AUC_{\tau, ss}/AUC_{\tau}$ ), and if data permit, CL,  $V_{ss, and}$  and  $t_{1/2}$ ;
- Peak and trough PF-06747143 concentrations for selected doses;
- Incidence of ADA and Nab against PF-06747143.

CCI

#### 3. INTERIM ANALYSES, FINAL ANALYSES AND UNBLINDING

No interim analysis or blinding is planned for this study. The final analysis will be conducted after the last subject last visit (LSLV).

#### 4. HYPOTHESES AND DECISION RULES

#### 4.1. Statistical Hypotheses

There are no statistical hypotheses. The emphasis of the final analyses will be on estimation of key summary statistics.

#### 4.2. Statistical Decision Rules

#### 4.2.1. Part 1

Decision rules are based on calculating unit probability mass (UPM) of three dosing intervals corresponding to under, proper, and over dosing in terms of toxicity. Specifically, the underdosing interval is defined as (0; pT-e1), the over-dosing interval (pT+e2), and the proper-dosing interval (pT-e1, pT+ e2), where e1 and e2 are small fractions. For a target DLT rate of 0.25, the target equivalence interval is (0.20, 0.30). The three dosing intervals are associated with three different dose-escalation decisions (Table 1). The under-dosing interval corresponds to a dose escalation (E), over-dosing corresponds to a dose de-escalation (D), and proper-dosing corresponds to remaining at the current dose (S). Given a dosing interval and a probability distribution, the unit probability mass (UPM) is defined as the ratio of the probability of the interval to the length of the interval. Once the safety assessment is complete for Cycle 1, the focus will be on allocation of new subjects to the dose most likely to be an MTD.

The study continues accruing until one of the three stopping conditions below is triggered. The algorithm will stop if any of the following criteria is met:

- 1. The maximum sample size has been achieved.
- 2. MTD has been identified with sufficient accuracy: at least 9 patients have been accumulated on a dose that is currently estimated to be the MTD, or
- 3. All doses explored appear to be overly toxic and the MTD cannot be determined.

Specifically the mTPI approach formalizes stopping rules as follow:

Rule 1 (early termination): if the first dose is too toxic  $\rightarrow$  Pr( $p_1 > p_T / data$ ) >  $\xi$  ;  $\xi = 0.975$ 

Rule 2 (dose exclusion), if dose= i is too toxic  $\rightarrow$  Pr( $p_i > p_T / data$ ) >  $\xi$  ;  $\xi = 0.975$  then exclude doses  $\geq i$ 

#### 4.2.2. Part 2

Part 2 of this study is intended to confirm the safety and tolerability of the dose selected in Part 1 while assessing the anti-leukemia activity of PF-06747143 in combination with standard dose of intensive chemotherapy. The DLT rate and its 95% confidence interval at the selected dose may be estimated. Part 2 data will also be used to determine the safey of combining PF-06747143 with standard chemotherapy in addition to justifying the efficacy of PF-06747143 monotherapy.

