#### 2.1. Study Overview

PF-06747143 will initially be developed in patients with acute myeloid leukemia (AML). The diagnosis of AML will be according to the World Health Organization (WHO) classification (Ref (8). The study will be conducted in two parts, Part 1 single agent dose escalation and Part 2 PF-06747143 in combination with standard chemotherapy with an option for single agent cohort expansion at the RP2D.

Assessment of anti-leukemia activity of PF-06747143 will be based on Diagnosis and management of acute myeloid leukemia in adults: recommendations from an international expert panel, on behalf of the European LeukemiaNet. (Ref (2).

#### 2.1.1. Part 1

Part 1, dose escalation, is an open-label, multi-center, single arm, non randomized, multiple dose, safety, pharmacokinetic and pharmacodynamic study of single-agent PF-06747143 in sequential dose levels of adult patients with refractory and/or relapsed AML in order to establish MTD/ RP2D or maximally permitted dose (MPD).

Patients will receive PF-06747143 as a weekly infusion (QW) in 28 day cycles at escalating doses. The proposed dosing scheme includes 0.3, 1.0, 3.0, 10, 15, and 20 mg/kg. Patients enrolled in the first two dose levels (0.3 mg/kg and 1.0 mg/kg) will be required to stay in the clinic/hospital overnight (minimum of 24 hours) after receiving the first dose of PF-06747143 to monitor for the potential risk of hyperleukocytosis that might be caused by the inhibition of by PF-06747143. On an individual basis, patients may be monitored overnight for the additional doses in Cycle 1 at the treating physician's discretion.

[figure not shown]
In the first three dose levels (ie, starting dose 0.3 mg/kg through 3.0 mg/kg), initiation of the first dose of PF-06747143 for each patient in the dose level must be at least 72 hours after the first dose of the previous patient. Patients enrolled in subsequent dose levels will be treated on an outpatient basis with no staggering of patients unless there are safety concerns based on findings at the lower doses.

Once MTD or MPD is identified, additional patients may be enrolled at that dose level (to a minimum of 9) to further investigate the anti-leukemia activity, safety, and PK profile of PF-06747143 prior to an expansion cohort with single agent PF-06747143 at the MTD/MPD/RP2D.

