The total estimated number of patients to be enrolled for the Part 1 dose escalation study will be approximately 30-50 patients but it is pertinent to recognize that the exact sample size of the mTPI design in Part 1 cannot be pre specified in advance because it is a dynamic feature of the design.

Once the dose of 15 mg/kg in Part 1 is found safe and tolerable, the Part 2 combination cohorts will be initiated at 10 mg/kg while the Part 1 single agent dose escalation continues to 20 mg/kg for MPD or MTD assessment.

Figure 1. Part I schema

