**Table 1. Possible Dose Levels** 

Dose Level	PF-06747143 Dose (mg/kg) (QW)
1	0.3
2	1.0
3	3.0
4	10
5	15
6	20

The mTPI method relies upon a statistical probability algorithm, calculated using all patients treated in prior and current cohorts at the same dose level to determine where future cohorts should be on dose escalation, no change in dose, or dose de escalation. The algorithm will stop if any of the following criteria is met:

- the maximum sample size has been achieved (approximately 50 patients total);
- at least 9 patients have been accumulated on a dose that is predicted to be the MTD;
   or
- all doses explored appear to be overly toxic and the MTD cannot be determined.

Although dose levels are capped at 20 mg/kg, this mTPI will continue to operate subject to the constraints detailed above while allowing for doses higher than specified. All clinically relevant adverse events (AEs) and serious adverse events (SAEs) will be reviewed by the Sponsor and Investigators after each dose level is complete to determine if the dose allocation schedule requires modification.

The modified toxicity probability interval (mTPI) design uses a Bayesian statistics framework and a beta/binomial hierarchical model to tailor dose-escalation and de-escalation decisions.(Ref 7) These rules are conceptually similar to those used by the 3+3 design and all thedose-escalation decisions for a given trial and can be pre-calculated under the mTPI design and presented in a two-way table (Appendix 4).

Patients will continue with study treatment until disease progression, patient refusal or unacceptable toxicity occurs. Patients experiencing a DLT may be managed with dose modification (after dose interruption) or discontinuation. Subsequent dose levels may not be opened until all patients entered at the current dose level have been treated and observed for at least one complete cycle and the number of DLTs among those patients in their first cycle has been determined. Intra-patient dose escalation will not be permitted in this study.

#### 2.2. Part 2

Part 2 dose expansion, is an open-label, multi-center, non randomized study to assess the safety and tolerability and preliminary anti-leukemia activity of PF-06747143 in three cohorts (two combination cohorts and one potential cohort of single agent PF-06747143).

Figure 2.

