#### 5. SAMPLE SIZE DETERMINATION

Approximately 125-140 patients are expected to be enrolled in this study (approximately 30-50 patients in Part 1 and 87-102 patients in Part 2).

The exact sample size of the mTPI design in Part 1 cannot be pre specified in advance because it is a dynamic feature of the design. The maximum sample size after which the Part 1 will be stopped and MTD declared is 30-50 patients. Also, a minimum of 9 patients is required to establish the MTD. The actual sample size of Part 1 will depend on the underlying dose toxicity profile and variability in actual data realization.

As for the number of patients treated at each dose, it is expected that the typical number will be 2 to 4 patients for the doses actually studied. For the dose declared as the MTD from Part 1, a minimum of 9 patients will be observed at this dose to further investigate the anti-leukemic activity, safety, and PK profile of PF-06747143. However, since not every dose listed will be studied and variable cohort size is allowed, the actual number of patients treated at each dose will vary.

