#### 7.2.2. MTD Definition

The MTD would be any doses with true toxicity probabilities in the Equivalence Interval (EI) where the EI is defined as [20%-30%].

In practice, the MTD will be the highest dose associated with the occurrence of DLTs  $\leq$ 33% (eg, 3/9 evaluable patients experience a DLT during the first treatment cycle).

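### With 0 or 1 DLT in 9 at 20 mg/kg, the SAP's working rule labels the top dose the MTD although its own algorithm rates it under-dosed; the dose cap and the Per Protocol set also need correcting

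*SAP*

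**What the plan says.** **Stopping.** Section 4.2.1 is closed: "The study continues accruing until one of the three stopping conditions below is triggered". The second condition is that "at least 9 patients have been accumulated on a dose that is currently estimated to be the MTD". The other two are the sample-size limit and excessive toxicity at every dose. Section 2.1.1.2 gives the same list. Section 5 adds: "The maximum sample size after which the Part 1 will be stopped and MTD declared is 30-50 patients".

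**MTD.** Section 7.2.2 first defines the MTD as a dose whose true DLT probability lies in 20-30%. It then gives a working rule: "In practice, the MTD will be the highest dose associated with the occurrence of DLTs" of at most 33%, with 3/9 as the example. No lower bound is set.

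**MPD.** Section 7.2.3 fixes it at 20 mg/kg for both parts. Section 2.1.1 treats it as a possible end of Part 1: "Once MTD or MPD is identified, additional patients may be enrolled at that dose level (to a minimum of 9", and the combination cohorts start "while the Part 1 single agent dose escalation continues to 20 mg/kg for MPD or MTD assessment".

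**Decision table.** For nine patients, Appendix 3 (Section 11.3) gives escalate (E) for 0-1 DLT, stay (S) for 2-3, de-escalate (D) for 4, and unacceptably toxic (DU) for 5 or more. It makes no exception at the top dose. Section 4.2.1 equates E with under-dosing.

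**Cap.** The relevant sentence of Section 2.1.1.2 opens "Although dose levels are capped at 20 mg/kg" but goes on to let the algorithm use doses above those listed. The same section allows additional dose levels without an upper limit.

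**Per Protocol set.** Section 6.2 limits it to patients dosed at the MTD level. Section 9.2.1 uses it to summarise DLTs, the Part 1 primary endpoint, at each dose level.

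**The concern.** Estimating the MTD is the Part 1 primary objective. A statement that the MTD is 20 mg/kg and a statement that the MTD was not reached up to 20 mg/kg are different conclusions. For a well-tolerated top dose, the SAP's working rule gives the first and its algorithm points to the second. The SAP does not say which to report, so the choice could be made after the data are seen.

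Two further defects lie nearby. The clause admitting higher doses contradicts the stated maximum. The Per Protocol restriction, read literally, removes most dose levels from the primary DLT summary.

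**Working it through.** **Inputs.** Target 0.25, interval 0.20-0.30 and the unit probability mass (UPM) rule, from Section 4.2.1. Working limit 33%, from Section 7.2.2. The SAP names a beta/binomial model but gives no prior in its text, so Beta(1,1) is an assumption.

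**Reproducing Appendix 3.** With x DLTs in n patients the posterior is Beta(1+x, 1+n-x). UPM is interval probability divided by interval length (0.20, 0.10 and 0.70), and the largest UPM decides. For 0 to 5 DLTs and n = 1 to 12 this reproduces every E/S/D boundary. At the stated exclusion threshold of 0.975, four DU cells come out as D (3/5, 4/7, 4/8, 5/10). None of them bears on this point.

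**Nine patients at 20 mg/kg.**
- 0/9, Beta(1,10): Pr(p<0.20) = 1 - 0.8^10 = 0.893. Pr(0.20<p<0.30) = 0.8^10 - 0.7^10 = 0.079. UPM: 0.893/0.20 = 4.46; 0.079/0.10 = 0.79; over-dosing 0.04. Decision E.
- 1/9, Beta(2,9): the distribution function is 1 - (1-p)^10 - 10p(1-p)^9, which is 0.624 at 0.20 and 0.851 at 0.30. Pr(0.20<p<0.30) = 0.227. UPM: 3.12; 2.27; 0.21. Decision E.
- 2/9: UPM 1.61; 2.95; 0.55. Decision S.
- 3/9: UPM 0.60; 2.30; 0.93. Decision S.

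The interval is narrow, so its probability alone does not separate the cases: it is 0.30 at 2/9 and 0.23 at 3/9. What separates them is the probability below 0.20, which is 0.89, 0.62, 0.32 and 0.12 for 0, 1, 2 and 3 DLTs.

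**Working rule on the same data.** 0/9 = 0% and 1/9 = 11.1%. Both are below 33% and no higher listed dose exists, so 20 mg/kg is labelled the MTD and the second stop is met. At 2/9 and 3/9 the working rule and the table agree.

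**How often, given nine patients at 20 mg/kg.** P(0 or 1 DLT) = (1-p)^9 + 9p(1-p)^8. At p = 0.25 this is 0.075 + 0.225 = 0.300. The last column takes cohorts of three, applies Appendix 3 at 3, 6 and 9 patients, leaves the dose on D or DU, and reads E at the cap as stay. Re-entry after de-escalation and cohorts of 2 or 4 are not modelled.

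| Assumed true DLT rate | 0-1 in 9 (label conflict) | Ends at nine on S (no conflict) |
|---|---|---|
| 5% | 93% | 6% |
| 10% | 77% | 19% |
| 15% | 60% | 31% |
| 20% | 44% | 39% |
| 25% | 30% | 43% |

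The first column of results is the same with or without those interim decisions, because 0-1 DLT never triggers D at 3 or 6 patients.

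**Per Protocol set.** Section 6.2 keeps one dose level (apart from any patient reduced to it from a higher dose), or nobody if no MTD is declared. Section 9.2.1 needs every level. Both cannot be followed.

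**The case against.** The strongest reply is that the plan already knows what to do. Section 2.1.1 names the MPD as an alternative end of Part 1 and allows filling that dose to nine, and Section 7.2.3 fixes its value. The SAP supplements a protocol, which may hold an operational criterion for the MPD. This stands as to intent. It does not remove the inconsistency inside the SAP, where the stopping lists, Section 5 and the working rule speak only of an MTD.

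A reader might infer that the SAP gives three incompatible instructions, or that Part 1 would run on to its sample-size limit. The text does not support either. Under the working rule the second stop ends accrual at nine patients before E is acted on, and Table 1 lists no dose for E to point to. Longer accrual would follow only if the 20-30% definition were applied literally.

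A reader might also take 93% to 30% as the chance that this trial meets the conflict. Those figures are conditional on nine patients being treated at 20 mg/kg, and the SAP gives no basis for the chance of getting there.

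The working rule is sometimes right: a true rate of 20% or 25% lies on or in the target interval, yet 0-1 DLT in 9 still occurs in 44% and 30% of such cases.

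On the cap, the sponsor and investigators review safety after each dose level, so actual dosing above 20 mg/kg should not be inferred from the clause. On the Per Protocol set, the rest of Section 6.2 discusses evaluability for the MTD assessment, which suggests that all levels were meant. The restriction remains wrong as worded.

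**Conclusion.** The SAP is wrong as written, with modest severity.

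First, with 0 or 1 DLT in 9 at 20 mg/kg the working rule declares an MTD that the plan's own algorithm rates as under-dosed. The posterior probability of the 20-30% interval is 0.08 (0/9) or 0.23 (1/9), and that of a rate below 20% is 0.89 or 0.62. Given nine patients at that dose, this result is the likelier of the two tabulated outcomes up to a true rate of about 20%, and the less likely at 25%. The consequence is a wrong label on the Part 1 conclusion. Dose choice is unaffected because 20 mg/kg is the ceiling either way, and the DLT counts remain visible in the listings. The posterior figures rest on the assumed Beta(1,1) prior; the E decision itself is printed in Appendix 3.

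Second, Section 2.1.1.2 contradicts the cap in Section 7.2.3.

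Third, as a separate error, the Per Protocol definition cannot support the by-dose summary of the primary endpoint.

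**What to change.** 1. Add a fourth stop to Sections 2.1.1.2 and 4.2.1: at least nine evaluable patients at 20 mg/kg with decision E. Report that the MTD was not reached up to the MPD, with the DLT rate and exact 95% interval (0/9: 0-34%; 1/9: 0.3-48%).
2. State that E at 20 mg/kg means stay.
3. Amend Sections 5 and 7.2.2 so that 20 mg/kg with decision E is not declared the MTD. The 33% rule can stay for lower doses bounded by a toxic next dose.
4. In Section 2.1.1.2, delete the clause admitting doses above those listed, and limit additional dose levels to at most 20 mg/kg.
5. In Section 6.2, delete the restriction to the MTD dose level.

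The cost is wording in the SAP and any matching protocol text, with no extra patients. The downside is that, given nine patients at 20 mg/kg, the report would say that the MTD was not reached in 44% of cases at a true rate of 20% and 30% at a true rate of 25%. The exact interval must therefore accompany the statement.

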#### 2.1.1.2. Criteria for Dose Escalation

A modified toxicity probability interval method (mTPI) (Ref (7)) targeting a DLT rate of 25% with an equivalence interval (20%-30%) will be utilized in order to estimate MTD in dose escalation. For all dose levels, patients may be enrolled in cohorts of 2-4 (the target size of each cohort will be 3 patients). Intermediate dose levels to further evaluate the safety and/or PK may be evaluated following discussion between sponsor and Investigator.

The dose levels planned for Part 1 of the study are shown in Table 1 Additional dose levels may be explored, if appropriate based on emerging safety, PK or PD data. Intra-patient dose escalation of PF-06747143 or the backbone chemotherapy (in Part 2 combination cohorts) will not be permitted.

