#### 11.3. Appendix 3. Detailed Dose Escalation/De-Escalation Scheme for mTPI Design

#### Number of Patients

#### Number of Toxicities

	1	2	3	4	5	6	7	8	9	10	11	12
0	E	E	E	E	E	E	E	E	E	E	E	E
1	D	D	S	S	S	S	E	E	E	E	Е	E
2		DU	D	D	S	S	S	S	S	S	S	S
3			DU	DU	DU	D	S	S	S	S	S	S
4				DU	DU	DU	DU	DU	D	S	S	S
5					DU	DU	DU	DU	DU	DU	D	S
6						DU						
7							DU	DU	DU	DU	DU	DU
8								DU	DU	DU	DU	DU
9									DU	DU	DU	DU
10										DU	DU	DU
11											DU	DU
12												DU

E=Escalate to the next higher dose
S=Stay at the current dose
D=De-escalate to the next lower dose
DU=The current dose is unacceptably toxic
Probability of target toxicity=0.25

Escalation/De-escalation algorithms for total number of patients treated at the current dose level (current and previous cohorts)

- With 2 patients treated at current dose level
  - o 0 DLT -> escalate
  - o 1 DLT -> de-escalate to the lower dose
  - 2 DLTs -> de-escalate and consider current dose as intolerable
- With 3 patients treated at current dose level
  - o 0 DLT -> escalate
  - o 1 DLT -> remain at the same dose
  - o 2 DLTs -> de-escalate
  - 3 DLTs -> de-escalate and consider current dose as intolerable
- With 4 patients treated at current dose level
  - o 0 DLT -> escalate
  - o 1 DLT -> remain at the same dose

- o 2 DLTs -> de-escalate
- 3-4 DLTs -> de-escalate and consider current dose as intolerable
- With 5 patients treated at current dose level
  - 0 DLT -> escalate
  - o 1-2 DLTs -> remain at the same dose
  - >= 3 DLTs -> de-escalate and consider current dose as intolerable
- With 6 patients treated at current dose level
  - o 0 DLT -> escalate
  - o 1-2 DLTs -> remain at the same dose
  - o 3 DLTs -> de-escalate
  - 4-6 DLTs -> de-escalate and consider current dose as intolerable
- With 7 patients treated at current dose level
  - o 0-1 DLT -> escalate
  - o 2-3 DLTs -> remain at the same dose
  - >= 4 DLTs -> de-escalate and consider current dose as intolerable
- With 8 patients treated at current dose level
  - o 0-1 DLT -> escalate
  - o 2-3 DLTs -> remain at the same dose
  - >= 4 DLTs -> de-escalate and consider currentdose as intolerable
- With 9 patients treated at current dose level
  - o 0-1 DLT -> escalate
  - o 2-3 DLTs -> remain at the same dose
  - o 4 DLTs -> de-escalate
  - 5-9 DLTs -> de-escalate and consider current dose as intolerable
- With 10 patients treated at current dose level
  - o 0-1 DLT -> escalate
  - o 2-4 DLTs -> remain at the same dose

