  - >= 5 DLTs -> de-escalate and consider current dose as intolerable
- With 11 patients treated at current dose level
  - o 0-1 DLT -> escalate
  - o 2-4 DLTs -> remain at the same dose
  - o 5 DLTs -> de-escalate
  - 6-11 DLTs -> de-escalate and consider current dose as intolerable
- With 12 patients treated at current dose level
  - o 0-1 DLT -> escalate
  - o 2-5 DLTs -> remain at the same dose

 6-12 DLTs -> de-escalate and consider current dose as intolerable

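### Section 4.2.1 sets the mTPI exclusion threshold at 0.975, but the Appendix 3 decision table follows 0.95: under a uniform prior, four cells printed as unacceptably toxic are plain de-escalation by the stated rule

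*SAP*

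**What the plan says.** Section 4.2.1 of the SAP sets the Part 1 decision rules. The target DLT rate is 0.25 and the equivalence interval is 0.20 to 0.30. Escalate, stay or de-escalate is chosen by the largest unit probability mass (UPM), meaning interval probability divided by interval length. Two stopping rules follow, both triggered when Pr(p > 0.25 | data) exceeds ξ = 0.975:

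- "Rule 1 (early termination): if the first dose is too toxic";
- "Rule 2 (dose exclusion), if dose= i is too toxic", in which case that dose and every higher one are excluded.

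Section 2.1.1.2 names a "beta/binomial hierarchical model to tailor dose-escalation and de-escalation decisions" and says the decisions can be calculated in advance and set out in a two-way table. It gives no prior parameters.

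That table is Appendix 3 (section 11.3), for 1 to 12 patients at a dose. It uses E, S, D and a fourth code, DU, for a dose that is unacceptably toxic. DU is printed at 3/5, 4/7, 4/8 and 5/10 (DLTs/patients). The bullets below the grid repeat this: for 5 patients, ">= 3 DLTs -> de-escalate and consider current dose as intolerable"; for 7 patients, ">= 4 DLTs -> de-escalate and consider current dose as intolerable", with the same cut-off for 8; for 10 patients, ">= 5 DLTs -> de-escalate and consider current dose as intolerable". The appendix states the target of 0.25 but no threshold of its own.

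**The concern.** A pre-calculated table should be what the stated rule produces. If the table was generated at a different ξ, the SAP contains two exclusion rules, and they disagree at particular DLT counts.

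The direction of dosing is not in dispute: D and DU both move down. What differs is what happens to the dose afterwards. Under D it stays open and the algorithm can return to it. Under DU it is judged intolerable and, read with Rule 2, it and all higher doses are closed. At the first dose, 0.3 mg/kg, the same difference decides whether Part 1 ends under Rule 1. DLT is the primary endpoint of Part 1 and the MTD is its purpose, so this should not be left to be settled after the DLTs have been seen.

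**Working it through.** **Inputs.** Target 0.25, interval (0.20, 0.30) and ξ = 0.975 come from section 4.2.1. The printed decisions come from the Appendix 3 grid and bullets. The grid row for 6 DLTs is broken in the text available to this review, so its cells were taken from the bullets; none of the disputed cells lies in that row. The prior is an assumption: Beta(1,1) first, then a wide search.

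**Formulas.** With x DLTs in n patients and a Beta(a, b) prior, the posterior is Beta(a + x, b + n − x). UPM is the posterior probability of each interval divided by its length: 0.20 for (0, 0.20), 0.10 for (0.20, 0.30) and 0.70 for (0.30, 1). The largest gives E, S or D. The decision becomes DU if Pr(p > 0.25 | data) > ξ. For Beta(1,1) that probability equals P(Bin(n + 1, 0.25) ≤ x).

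**Reproducing the table.** With Beta(1,1) and ξ = 0.95, all 90 cells agree with Appendix 3. With ξ = 0.975, 86 agree and four do not.

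**One cell by hand, 3/5.** P(Bin(6, 0.25) ≤ 3) = (729 + 1458 + 1215 + 540)/4096 = 3942/4096 = 0.9624. This is above 0.95 and below 0.975. The UPMs are 0.085, 0.535 and 1.328, so the decision without exclusion is D.

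**Cells near the thresholds, Beta(1,1):**

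| DLTs/n | Pr(p > 0.25) | Printed | ξ = 0.95 | ξ = 0.975 |
|---|---|---|---|---|
| 5/11 | 0.9456 | D | D | D |
| 2/3 | 0.9492 | D | D | D |
| **4/8** | 0.9511 | DU | DU | **D** |
| **3/5** | 0.9624 | DU | DU | **D** |
| **5/10** | 0.9657 | DU | DU | **D** |
| **4/7** | 0.9727 | DU | DU | **D** |
| 6/12 | 0.9757 | DU | DU | DU |
| 5/9 | 0.9803 | DU | DU | DU |

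Under this prior the printed table requires ξ between 0.9492 (2/3, the largest value not printed DU) and 0.9511 (4/8, the smallest printed DU).

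**Does another prior rescue 0.975?** All Beta(a, b) with a from 0.05 to 4 and b from 0.05 to 8 in steps of 0.05 were tried, 80 × 160 = 12,800 priors. At ξ = 0.975 none reproduces the table; the smallest number of mismatches is 3. Beta(0.75, 0.40), for example, still fails at 3/5, 4/8 and 5/10. At ξ = 0.95 exactly one prior on the grid gives no mismatch: Beta(1,1).

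**Can the cells be reached?** Fully evaluable cohorts of exactly 3 give n = 3, 6, 9 and 12 and never reach them. But section 2.1.1.2 says "patients may be enrolled in cohorts of 2-4 (the target size of each cohort will be 3 patients". Using only Stay decisions in the table:

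- 1/3, then 2 DLTs in 2 patients, gives 3/5;
- 1/3, then 3 in 4, gives 4/7;
- 1/4, then 3 in 4, gives 4/8;
- 1/3, then 2/6, then 3 in 4, gives 5/10.

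Section 6.2 makes replacement of non-evaluable patients optional, so n = 5 or 8 can also arise when cohorts of 3 were planned.

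**The case against.** The strongest reply is that little turns on this. Both versions de-escalate, and the printed table is the more cautious. Sites would naturally work from the table, which spells out an action for each count, and section 2.1.1.2 adds sponsor and investigator review after each dose level. The cells are also uncommon. For a single dose, with cohort sizes drawn equally from 2, 3 and 4 (an assumption) and accrual only through Stay decisions, a disputed cell is reached in about 2% of cases at a true DLT rate of 0.30 and about 4 to 5% at 0.40 to 0.60. All of this stands, and it limits the weight of the point.

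It can also be said that the count of four rests on an assumed prior. That is right as far as it goes: four is the count under Beta(1,1), and across the priors searched the firm statement is at least three. The conflict itself remains under all of them.

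Finally, Appendix 3 does not itself mention closing higher doses or ending Part 1. Those consequences come from reading DU as the outcome of Rules 1 and 2. That reading is an inference, but a natural one, because section 4.2.1 offers no other rule that would generate DU. Nor does habitual use of the table settle the matter: section 4.2.1 presents Rules 1 and 2 as the formal stopping rules, and no sentence says which passage prevails.

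**Conclusion.** The inconsistency is real. Section 4.2.1 states 0.975, and Appendix 3 is exactly what 0.95 gives with a uniform prior. Under that prior, 3/5, 4/7, 4/8 and 5/10 are printed DU but are D by the stated rule; under every other prior searched, at least three cells conflict with 0.975. The perfect match at 0.95 strongly suggests that the table was generated at 0.95 and that the number in the text is the slip, though the SAP alone cannot prove which was intended.

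The effect is confined to whether a dose, and those above it, are closed, and at 0.3 mg/kg to whether Part 1 stops. It does not make dosing by the printed table less safe. It should be corrected because it concerns a stopping rule and can be settled before the data arise.

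**What to change.** Choose one of two corrections:

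- set ξ to 0.95 in Rules 1 and 2 of section 4.2.1, which leaves Appendix 3 as printed; or
- keep 0.975 and change 3/5, 4/7, 4/8 and 5/10 from DU to D in the grid, with matching changes to the bullets for 5, 7, 8 and 10 patients.

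In either case add one sentence stating the prior, Beta(1,1) if that was used. The cost is one number in two rules, or four cells and four bullets, plus that sentence, with the protocol aligned if it repeats them.

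As an optional clarification, not part of the inconsistency: a sentence could say that Stay is an allocation decision and that the 33% criterion in section 7.2.2 governs declaration of the MTD, so that Stay at 4/10, 4/11 or 5/12 is not read as making that dose the MTD.
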